## fit the model
## response: AUC48
## Fixed Effects: Treatment, Period
## Random Effects: Sequence
fit <- lmer(AUC48 ~ Treatment + (1|seq) +
  'Visit Period',
  data=dat, REML = FALSE)
```

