1.3 Methodology for Crossover Studies

In crossover studies, measurements are repeated across treatments. Each subject receives each treatment with a washout period in between. We will use a toy example where Y_{ijkl} is the outcome, i denotes the subject, j denotes the treatment, k denotes the period, and l denotes the sequence. For four treatments, A, B, C, D, there are a number of different treatment sequences (e.g. ABCD, ACDB, BACD) and four periods. We account for variability from sequences and periods in the model. An example of a crossover model is the following:

$$Y_{ijkl} = \mu + \delta_l + \beta_{i(l)} + \alpha_j + \gamma_k + \alpha_{j|k} + \varepsilon_{ijkl} \quad (3.1)$$

where, μ is the overall mean, fixed sequence effect is δ_l , fixed treatment effect is α_j , fixed period effect is γ_k , and $\beta_{i(l)}$ is the random individual subject effect for individual i nested in the sequence l . The fixed interaction between treatment and period is $\alpha_{j|k}$ and the random error from the realization process or measurement error is ε_{ijkl} . For the random effects, we assume $\beta_{i(l)}$ is independent of ε_{ijkl} and we have flexibility in modeling the random errors. For example, it may be reasonable for the residual error to have different variances based on treatment: $Var(\varepsilon_{i1kl}) \neq Var(\varepsilon_{i2kl})$. Naturally, one could add additional fixed effects for covariates or interactions between covariates and treatments. Mean and covariance parameters are typically estimated through maximum likelihood estimation (MLE). In SAS, PROC MIXED is a popular procedure to fit these mixed effects models. Sophisticated inference including adjustments for multiple comparisons can be carried out with PROC MIXED. In R, the nlme and lme4 [1] packages can be used to fit the models. The lmerTest package is a popular companion to lme4 for statistical inference [3].

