2.2 Fitting the Model

The toy dataset provided serves to illustrate the proposed methodology of the actual analysis. The dataset contains PK parameters from 15 subjects participating in a crossover design study with three periods and two treatment groups, a blueberry treatment and a control group. At each period, subjects had concentrations of 15 different metabolites measured via blood and urine samples. Concentrations were converted to corresponding pharmacokinetic parameter using an appropriate PK model. The primary purpose of the study was to compare the bioavailability of the ten metabolites between the blueberry treatment and the control group.

We propose the following model for analysis:

$$Y_{ijkl}^n = \mu + \delta_l^n + \alpha_j^n + \gamma_k^n + (\alpha\gamma)_{jk}^n + \varepsilon_{ijkl} \quad (2.1)$$

Below are detailed descriptions of each term in the model:

- μ : Overall mean.
- δ_l^n : Sequence Effect for metabolite n .
- α_j^n : Fixed treatment effect for metabolite n .
- γ_k^n : Period effect for metabolite n .
- $\alpha\gamma_{jk}^n$: Interaction between treatment and period for metabolite.
- ε_{ijkl} : Random error from the realization process or measurement error.

The effects δ_l^n , γ_k^n , and $\alpha\gamma_{jk}^n$ can be considered fixed or random. We assume the random effects are independent of each other. Here the response Y_{ijkl} , represents the bioavailability of metabolite n . Additionally, i denotes the i -th subject in the dataset. If we are interested in the model for just one metabolite, we can subset the dataset to just include observations for that one metabolite and then fit a similar, smaller model. An example is:

$$Y_{ijkl} = \mu + \delta_l + \alpha_j + \gamma_k + \varepsilon_{ijkl} \quad (2.2)$$

Below are detailed descriptions of each term in the model:

- μ : Overall mean.
- δ_l : Sequence Effect.
- α_j : Fixed treatment effect.
- γ_k : Period effect.
- ε_{ijkl} : Random error from the realization process or measurement error.

Notice this is the same model as before without the interaction, but without the n superscripts, since we only have one metabolite of interest.

This model can be fit using the `lmer` function in the `lme4` package of R. We will use the smaller model with just one metabolite for demonstration. To add the effect of one variable, `X_1`,

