2.3 Interpreting Model Output

Using the lmerTest package in R, we can conduct hypothesis tests for fixed and random effects in linear mixed effects models. The anova function provides F-tests on the fixed effects, letting you evaluate if a fixed effect is useful for explaining the response. Using the above model, the anova output is as follows:

```
> anova(fit)
Type III Analysis of Variance Table with Satterthwaite's method
  Sum Sq Mean Sq NumDF DenDF F value    Pr(>F)
Treatment  158.70 158.70     1 177.99 17.746 4.005e-05 ***
'Visit Period' 391.38 195.69     2 178.34 21.883 3.170e-09 ***
---
Signif. codes:  0 '***' 0.001 '**' 0.01 '*' 0.05 '.' 0.1 ' ' 1
```

Based on this, we can see that both treatment and period are useful for explaining the response. Since treatment is binary (control, treatment) here, we can examine if administering the treatment increases or decreases the response, on average. The summary function is one way to do this. Below is selected output:

```
> summary(fit)
Fixed effects:
  Estimate Std. Error    df t value Pr(>|t|)    
(Intercept)  0.02752  0.84451 4.24374  0.033  0.975
TreatmentTreatment 1.91665  0.45498 177.99167  4.213 4.00e-05 ***
'Visit Period'B -0.29409  0.55514 178.22795 -0.530  0.597
'Visit Period'C  3.24513  0.63618 178.66646  5.101 8.57e-07 ***
```

Notice the estimate for the TreatmentTreatment is 1.91665. This indicates the model the model estimates a 1.91655 increase in AUC if the Treatment is administered instead of the control. The corresponding p-value is small, so we can be confident that the treatment increases AUC, on average. To check if the random effects are useful for explaining the response. Since we are not interested in specific levels of the random effects, we just want to check if considerably variation is coming from the random effects. The ranova function runs a hypothesis testing the variance against zero. For the ANOVA model, here is the output:

```

> ranova(fit)
ANOVA-like table for random-effects: Single term deletions

Model:
AUC48 ~ Treatment + 'Visit Period' + (1 | seq)
      npar  logLik   AIC   LRT Df Pr(>Chisq)
<none>      6 -454.87 921.74
(1 | seq)    5 -460.85 931.70 11.969  1  0.000541 ***
---
Signif. codes:  0 '***' 0.001 '**' 0.01 '*' 0.05 '.' 0.1 ' ' 1

```

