## combine datasets to make a subject ID and sequence dataset
seq_dataset <- bind_cols(int1,int2) %>%
  unite(seq,trt1,trt2) %>%
  select('Subject ID',seq)

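### With the SAP's random subject effect in the model, maximum likelihood fitting makes treatment standard errors about 4% too small; restore that effect and switch to REML together

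*SAP*

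**What the plan says.** SAP 1.3 sets out a crossover model, labelled (3.1), with fixed sequence, treatment and period effects, a treatment-by-period interaction, and a term that "is the random individual subject effect for individual i nested in the sequence". On estimation it says: "Mean and covariance parameters are typically estimated through maximum likelihood estimation (MLE"). Section 1.4 makes a model numbered (1.1) the framework for the treatment tests. No equation carries that number, and I read it as the model of 1.3.

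Section 2.2 proposes model (2.1) and a smaller model (2.2). Neither contains a subject term. The code for the smaller model begins "fit <- lmer(AUC48 ~ Treatment + (1|seq") and ends with "data=dat, REML = FALSE"; the Code Appendix repeats the call. Sequence is therefore the only random effect. The appendix builds it with "unite(seq,trt1,trt2"), that is, from the first two treatments received.

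Section 2.3 takes Satterthwaite F- and t-tests from this fit. The SAP calls the code an illustration ("We will use the smaller model with just one metabolite for demonstration"), but section 2.2 also says that the toy data illustrate the method of the real analysis. No other fitting specification is given. The SAP does not say why ML was chosen, and it states no significance level.

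**The concern.** ML estimates the residual variance without allowing for the fixed effects that were fitted, so the estimate is biased downwards. Satterthwaite df computed from an ML fit are also too large. Both errors push p-values down. REML corrects the variance by removing the fixed-effect degrees of freedom from the divisor.

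The usual reason to prefer ML is a likelihood comparison of models with different fixed effects, and the SAP makes none. Its one likelihood-ratio test, in section 2.3, drops a random effect and does not need ML. The same call would be reused for each metabolite and PK parameter, and section 1.4 leaves multiplicity control open, so a small bias would recur across many tests.

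**Working it through.** **1. The toy output.** Section 2.3 reports the treatment estimate, SE and df as "1.91665 0.45498 177.99167" and the F-test as "177.99 17.746 4.005e-05".

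- t = 1.91665 / 0.45498 = 4.213; F = t² = 17.746; p on 177.99 df = 4.005e-05. The printed figures reproduce.
- Section 2.3 describes two sequences. A df of 178 then equals N − 2 with N = 180 rows, with nothing removed for the three fixed-effect df (one treatment, two period). The printed log-likelihood also fits N of about 180. The row count is inferred, not stated; 15 subjects × 3 periods would give 45, and the SAP does not explain the difference.
- Under REML the divisor would be 178 − 3 = 175. SE ratio ML/REML = √(175/178) = 0.992; REML SE = 0.45498 / 0.992 = 0.459; t = 4.18; p = 4.7e-05. On this output, ML alone moves a 5% test to about 5.2%.

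**2. The planned trial with a random subject effect.** Inputs: four periods and 28 participants (SAP 1.1); 24 expected completers (protocol, participant numbers). Assumptions: two-sided 5%, complete data, one row per participant-period. With n participants there are 4n rows, and removing n subject levels leaves 3n. Treatment and period take 3 + 3 = 6 df.

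- ML divisor and df: 3n. REML: 3n − 6.
- SE ratio = √((3n − 6)/3n).
- Contrast type I error = P(|t on 3n − 6 df| > t₀.₉₇₅,₃ₙ × SE ratio).
- 3-df type I error = P(F on 3 and 3n − 6 df > F₀.₉₅,₃,₃ₙ × SE ratio²).

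| n | ML / REML df | SE ratio | Contrast | 3-df F |
|---|---|---|---|---|
| 24 | 72 / 66 | 0.957 | 6.1% | 6.7% |
| 28 | 84 / 78 | 0.964 | 5.9% | 6.4% |

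For n = 24 the contrast critical value is 1.9935 × 0.9574 = 1.909 on 66 df, giving 6.1%. The F critical value is 2.732 × 0.9167 = 2.504 on 3 and 66 df, giving 6.7%.

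**3. Adding a fixed treatment-by-period interaction, n = 24.** How many of its 9 df fall within participants depends on the sequences used, which the documents do not list.

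- All 9 within participants: 57/72, SE ratio 0.890, type I error 8.1% and 10.2%.
- Four-sequence Latin square (6 within, 3 confounded with sequence): 60/72, SE ratio 0.913, type I error 7.4% and 8.9%.

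**4. The model exactly as coded.** Take 24 participants in four balanced sequences, total variance 1 and intraclass correlation (ICC) ρ, with the sequence variance estimated above zero. The residual now pools 66 within-participant df, with expectation 1 − ρ, and 20 between-participant df, with expectation (1 − ρ) + 4ρ. ML divides the pooled sum of squares by 96 − 4 = 92:

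- Expected residual variance = (86(1 − ρ) + 80ρ)/92 = (86 − 6ρ)/92. The correct value is 1 − ρ.
- The two are equal at ρ = 6/86 = 0.07. With 12 sequences of two, (78 − 30ρ)/84 = 1 − ρ gives ρ = 6/54 = 0.11. Above this the SE is too large.
- At ρ = 0.5 the SE is √(83/46) = 1.34 times the true value. REML divides by 86 instead of 92, so it enlarges the SE further: √(83/43) = 1.39.

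**5. Simulation under the null.** 24 participants, four balanced sequences, 6,000 trials per setting, df set by formula. Monte Carlo standard error at 5% is √(0.05 × 0.95/6000) = 0.3 points. Entries are 3-df F / contrast.

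| ICC | Sequence only, ML | Sequence only, REML | Subject, ML | Subject, REML |
|---|---|---|---|---|
| 0 | 6.1 / 5.8% | 4.6 / 4.9% | 6.7 / 6.2% | 5.1 / 5.2% |
| 0.1 | 5.4 / 4.7% | 4.1 / 4.1% | 7.2 / 5.8% | 5.7 / 5.1% |
| 0.3 | 2.1 / 2.7% | 1.4 / 2.2% | 6.4 / 5.9% | 4.8 / 4.8% |
| 0.5 | 0.4 / 1.2% | 0.3 / 1.0% | 6.7 / 6.1% | 4.9 / 5.2% |
| 0.7 | 0.07 / 0.13% | 0.03 / 0.08% | 7.0 / 5.8% | 4.9 / 4.7% |

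**The case against.** A reader might infer from the `REML = FALSE` argument that every treatment test in this SAP runs above its nominal level. The documents do not support that. The call as written has no subject effect, so with shared sequences between-participant variance enters the residual and the test falls below 5% at any material ICC. As the appendix builds the variable, four treatments give at most 4 × 3 = 12 sequence levels, so 24 or 28 participants must share them. The ML inflation would return under the sequence-only model if the variable used the full order and each participant had a different one, because sequence would then stand in for subject. In the coded model, changing only the estimator makes a conservative test slightly more so. All of this stands, and it is why the two edits belong together.

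It is also fair that the code is a demonstration, that section 1.3 describes ML as typical without committing to it, and that the toy p-value barely moves. That lowers the severity. It does not remove the point, because the SAP offers the example as the pattern for the real analysis and gives no other. The interaction figures are conditional too: section 2.2 lets that term be fixed or random, and the code leaves it out. Finally, the SAP specifies no confidence intervals, so the evidence concerns standard errors and p-values.

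**Conclusion.** The point holds for the model the SAP should be fitting, the crossover model of section 1.3 with its random subject effect. There ML understates treatment standard errors by 4.3% (24 completers) or 3.6% (28) and turns an assumed two-sided 5% test into one of about 6–7%. With a fixed interaction and 24 completers the range is 7.4–8.1% for a contrast and 8.9–10.2% for the 3-df test. These figures rest on complete, balanced data with one row per participant-period; dropouts would make them approximate. The inflation does not depend on the ICC.

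For the model as coded the direction depends on the ICC and on how participants share sequences, neither of which the documents give. The missing subject effect is the larger defect. Correcting it while keeping ML would replace a conservative test with a mildly liberal one. Severity is minor to moderate.

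**What to change.** In the fitting call in section 2.2 and in its copy in the Code Appendix, make two changes together: add a random intercept for participant, as in the model of section 1.3, and set `REML = TRUE`. Add the subject term to models (2.1) and (2.2) so that text and code agree. State in section 1.3 that inference uses REML with Satterthwaite or Kenward-Roger degrees of freedom, and that ML is kept only for likelihood comparison of models with different fixed effects.

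The cost is one argument, one model term and a sentence or two of text. In the correctly specified model, p-values will be slightly larger than under ML. Changing the estimator without the subject term is not a repair.

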2.3 Interpreting Model Output

Using the lmerTest package in R, we can conduct hypothesis tests for fixed and random effects in linear mixed effects models. The anova function provides F-tests on the fixed effects, letting you evaluate if a fixed effect is useful for explaining the response. Using the above model, the anova output is as follows:

```
> anova(fit)
Type III Analysis of Variance Table with Satterthwaite's method
  Sum Sq Mean Sq NumDF DenDF F value    Pr(>F)
Treatment  158.70 158.70     1 177.99 17.746 4.005e-05 ***
'Visit Period' 391.38 195.69     2 178.34 21.883 3.170e-09 ***
---
Signif. codes:  0 '***' 0.001 '**' 0.01 '*' 0.05 '.' 0.1 ' ' 1
```

Based on this, we can see that both treatment and period are useful for explaining the response. Since treatment is binary (control, treatment) here, we can examine if administering the treatment increases or decreases the response, on average. The summary function is one way to do this. Below is selected output:

```
> summary(fit)
Fixed effects:
  Estimate Std. Error    df t value Pr(>|t|)    
(Intercept)  0.02752  0.84451 4.24374  0.033  0.975
TreatmentTreatment 1.91665  0.45498 177.99167  4.213 4.00e-05 ***
'Visit Period'B -0.29409  0.55514 178.22795 -0.530  0.597
'Visit Period'C  3.24513  0.63618 178.66646  5.101 8.57e-07 ***
```

Notice the estimate for the TreatmentTreatment is 1.91665. This indicates the model the model estimates a 1.91655 increase in AUC if the Treatment is administered instead of the control. The corresponding p-value is small, so we can be confident that the treatment increases AUC, on average. To check if the random effects are useful for explaining the response. Since we are not interested in specific levels of the random effects, we just want to check if considerably variation is coming from the random effects. The ranova function runs a hypothesis testing the variance against zero. For the ANOVA model, here is the output:

```

> ranova(fit)
ANOVA-like table for random-effects: Single term deletions

Model:
AUC48 ~ Treatment + 'Visit Period' + (1 | seq)
      npar  logLik   AIC   LRT Df Pr(>Chisq)
<none>      6 -454.87 921.74
(1 | seq)    5 -460.85 931.70 11.969  1  0.000541 ***
---
Signif. codes:  0 '***' 0.001 '**' 0.01 '*' 0.05 '.' 0.1 ' ' 1

```

This tells us that there is considerable variation between sequences. Some quick summary statistics show us the mean AUC for the control then treatment sequence is 2.80 and the treatment then control sequence is 0.50 (note this is just for this metabolite, not all metabolites like the plot in 2.1). This intuitively shows why the sequence effect has a small p-value.

3 Code Appendix

First, we present the code for the plots.

```

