1.4 Proposed Methodology for Crossover Longitudinal Studies

The model specified in (1.1) will serve as a framework for testing the differences of fixed effects between treatments. Using the methodology outlined in Section 1.2, the appropriate PK parameters for a given metabolite (ex. Bioavailability) will be calculated. The PK parameters will be represented as the continuous responses Y_{ijkl} in the model. Note that each measured PK parameter is specified to a given subject I receiving treatment j at a specified period k within sequence l .

It is of primary interest to test the potential differences in bioavailability of blueberry-derived metabolites across treatments. Given the number of metabolites being tested, multiple comparison adjustments will be necessary. There are a multitude of strategies for tackling such problems each with their respective advantages and disadvantages. However, given the relatively small sample size ($n=28$), controlling the family-wise error rate (FWER) across all metabolites

may drain requisite statistical power needed to detect any difference between treatments. It may be beneficial to set up a smaller subset of metabolites prior to analysis that are of primary interest and then investigate differences between the remaining metabolites in an exploratory nature.

[figure not shown]
2 Recommended Analysis/Design

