## subset dataset
dat <- plasma %>% filter(Metabolite=="1-M-Xan_108Q")

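### The SAP's worked single-metabolite fit rests on about 180 rows where its own description allows 45, and neither the models proposed for use nor the code has a participant term or a row check

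*SAP*

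**What the plan says.** SAP 2.2 offers the example as an illustration of how the actual analysis will be done. It describes the data this way: "The dataset contains PK parameters from 15 subjects participating in a crossover design study with three periods and two treatment groups". The fit is confined to one metabolite: "We will use the smaller model with just one metabolite for demonstration". The code appendix filters the plasma data to that metabolite and does nothing else to the rows. SAP 2.3 repeats the restriction when it discusses the sequence means: "note this is just for this metabolite, not all metabolites like the plot in 2.1".

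SAP 1.4 sets the unit of analysis: "each measured PK parameter is specified to a given subject I receiving treatment j at a specified period k within sequence l". That is one value per participant and period for a given metabolite.

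The fitted model is "AUC48 ~ Treatment + 'Visit Period' + (1 | seq"), estimated by maximum likelihood ("data=dat, REML = FALSE"). The general crossover model (3.1) in SAP 1.3 has a random subject effect nested in sequence. Models (2.1) and (2.2) and the `lmer` call do not. SAP 2.3 prints "177.99 17.746 4.005e-05" for treatment and reads it as good evidence that treatment raises AUC.

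**The concern.** AUC48 summarises a whole concentration curve, so a participant has one per period and metabolite. A denominator df near 178 cannot come from 45 such values. The SAP does not remark on the gap.

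The example matters because it is the only executable specification of the trial's main comparison, the difference in bioavailability between treatments. If trial AUCs were held on several rows (for example one per sample or visit day), this code would run without complaint and treat the repeats as new information. Even with one row per participant-period, the code would treat four values from one person as unrelated except through sequence.

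**Working it through.** **Inputs.** SAP 2.2: 15 subjects, 3 periods, 2 treatments, 1 metabolite in the fit. SAP 2.3: treatment mean square 158.70, F 17.746, df 177.99, SE 0.45498; period SEs 0.55514 and 0.63618; log-likelihood -454.87; sequence means 2.80 and 0.50.

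**1. Reproduce the printed test.** F = 17.746 on 1 and 177.99 df gives p = 4.005e-05, as printed. The output is internally consistent.

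**2. Rows the description allows.** 15 × 3 × 1 = 45. On the generous assumption that each period holds two treatment days, 90.

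**3. Rows from the df.** I rebuilt the Satterthwaite df for this model under maximum likelihood with two sequences. On 45 rows the treatment and period df are about 43 to 45; on 180 rows they are about 178 to 180. The printed values are 177.99 and 178.34.

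**4. Rows from the log-likelihood.** Residual variance s² = 158.70/17.746 = 8.943. Under maximum likelihood, -2 logL = n[ln(2πs²) + 1] + Σ ln(1 + n_s·v/s²), summed over sequences, where v is the sequence variance. The SAP does not print v. I assume the squared half-difference of the sequence means, ((2.80 - 0.50)/2)² = 1.32. The bracket equals 5.029.

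| n | n × 5.029 | sequence term | logL |
|---|---|---|---|
| 45 | 226.3 | 2.9 | -114.6 |
| 90 | 452.6 | 4.1 | -228.3 |
| 180 | 905.2 | 5.3 | -455.2 |

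The printed value is -454.87. Solving for n gives 179.5 to 180.2 with two sequences and v from 0.5 to 3, and 178.0 to 180.2 if the number of sequences also varies from 2 to 6.

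**5. Rows from the treatment SE.** With an even treatment split, SE = 2s/√n: 0.892 for 45 rows and 0.446 for 180. Printed: 0.455.

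**6. Illustration: even copying.** 180/45 = 4 rows per subject-period. If these were exact copies and the residual variance stayed the same, F = 17.746/4 = 4.44 on about 43 df, p = 0.041. With 90 genuine values and two copies, F = 8.87 on about 88 df, p = 0.004.

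**7. Does an even layout fit the output?** No. Sixty rows per period with treatment balanced gives both period SEs as √(8.943 × 2/60) = 0.546. Imbalance could raise this, but the treatment SE limits it:
- SE 0.45498 requires a within-period treatment sum of squares of at least 8.943/0.2070 = 43.2, out of a maximum of 45.
- The treated fractions p in the three periods therefore satisfy Σ(p - 0.5)² ≤ 1.8/60 = 0.030.
- The squared difference between two periods is then at most 0.060, so a period SE is at most √(0.2981 + 0.060 × 0.2070) = 0.557.

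The printed 0.555 fits and 0.636 does not. Repetition is uneven, some periods are incomplete, or the data are not what SAP 2.2 describes.

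**8. Effect of a participant term.** Take step 6's F of 4.44 and assume a within-participant correlation (ICC), with F/(1 - ICC) on 27 df. Then p is 0.045 at ICC 0, 0.006 at 0.5, 0.0007 at 0.7 and 0.00007 at 0.8. It equals the printed p at ICC of about 0.815 and is smaller above that.

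**9. Correct df in this trial.** For complete data, treatment and period fixed and participant random, REML gives 4n - n - 6: 66 for 24 participants and 78 for 28. Under the SAP's `REML = FALSE` the Satterthwaite df is 3n: 72 and 84.

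**The case against.** The strongest reply is that duplication is only one explanation. SAP 2.2 is careless about its own example: it gives 15 metabolites and later ten, and three periods although the appendix code builds sequence from two visits. About 180 distinct rows, from more subjects or several distinct AUCs per subject, would give the same df. This stands. The documents cannot decide between the explanations, and step 7 excludes the simplest form of copying.

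A reader might infer that the p-values are shown to be far too small. The documents do not support that. It holds if values were duplicated and the model is kept as fitted. With a participant term the answer depends on a correlation that is not given. If the rows are distinct crossover observations, leaving that term out often makes the treatment SE too large.

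It is also fair to say that this is a toy example, that no trial result rests on it, and that SAP 1.4 and model (3.1) already imply the right unit and the participant effect. That lowers the stakes without removing the point, because the models actually proposed and the code carry out neither.

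**Conclusion.** The inconsistency is firm. The df, log-likelihood and treatment SE agree on about 180 rows, against at most 45 (or 90 on the generous reading). The only added assumption, the sequence variance, barely moves the count. The cause is not known, so neither the size nor the direction of the error in 4.0e-05 can be stated. The p of about 0.04 is an illustration under even copying, which the printed SEs contradict.

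Two gaps hold whichever explanation is true. The proposed models and code omit the participant effect, so all rows (about 180, from 15 people by the SAP's account) count as independent apart from sequence. Nothing in the code enforces the unit set in SAP 1.4.

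A reader might also infer an inflated type I error for the trial. If each trial AUC were stored in exactly two or four copies and participant were modelled, the SE would shrink to √(78/190) = 0.64 or √(78/414) = 0.43 of its proper value, and a 5% test of one contrast would reject 21% or 40% of the time. Nothing in either document says trial AUCs will be stored that way, so these figures are conditional and not a finding about this trial.

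**What to change.** - Before the `lmer` call, reduce the data to one row per participant, period, metabolite and sample matrix, and state that unit in SAP 2.2.
- Add the participant random effect, `(1|Subject ID)` with the column name quoted as R requires, to models (2.1) and (2.2) and to the code, in line with model (3.1).
- Add a check to each fit: no more than 4 × participants rows (112 for 28). For model (2.2) with complete data, treatment df should be about 66 (24 participants) to 78 (28) under REML, or 72 to 84 if `REML = FALSE` is kept. Name the estimation method next to the range, because a correct maximum-likelihood fit on 28 participants would fail the REML range.
- Explain the roughly 180 rows in the example, or replace the output with a fit that matches its description.

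The cost is a few lines of code, short edits to two model statements, and one or two sentences in the SAP. No change to design or data collection is needed.
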